Statistical **Study Populations: Considerations** • Safety & Tolerability Population: All enrolled subjects who have received at least 1 dose of IP (belnacasan or placebo) will be studied. Even if subjects have discontinued study treatment, as long as they maintain consent, they will continue to be in the study and included in analysis, i.e., their safety and tolerability information will continue to be collected for at least 60 days. • Treatment Effect Evaluable Populations: All enrolled subjects who have received at least 1 dose of IP (belnacasan or placebo) will be studied. Even if subjects have discontinued study treatment, as long as they maintain consent, they will continue to be in the study and included in analysis, i.e., their outcome information will continue to be collected for at least 60 days. **Analysis Methods:** FDA Data Standard Guidelines will be followed. Continuous variables will be summarized using the number of observations, number of observations above the limit of quantification (if applicable), mean, standard deviation (SD) median, and range. Categorical variables will be summarized using frequency counts and percentages. Comparison of belnacasan and placebo groups will utilize Poisson regression for counts, Cox proportional hazards regression for time-to-event data and mixed effects models for continuous and categorical data obtained over study days. **Primary Safety and Tolerability Analysis:** All safety & tolerability analyses will be performed on the Safety Population. The safety data will be presented in individual listings and summary tables. Overall safety will be assessed by the number of belnacasan dosed subjects experiencing a grade 4 or 5 SAE during the trial. Of 20 subjects enrolled in the belnacasan group, 3 or more developing grade 4 or 5 SAE probably related to belnacasan would be considered unlikely due to chance. Therefore, belnacasan will be determined safe if no more than 2 subjects develop a grade 4 or 5 SAE in the belnacasan group probably related to belnacasan. In terms of stopping rules, should two or more subjects develop a similar Grade 3 SAE that is at least possibly related to belnacasan or should one or more subjects develop a \geq Grade 4 SAE that is at least possibly related to belnacasan, the trial will be paused for DSMB safety review. **Secondary Treatment Effect Endpoint Analysis:** Event counts over 60 days will be analyzed by Poisson regression. Time to events will be analyzed by Cox regression. Differences between belnacasan and placebo with respect to change in continuous endpoints will be assessed by mixed effects models for continuous repeated measures data and mixed effects logistic models for repeated categorical variables. Endpoint proportions of belnacasan and placebo groups will be assessed by contingency table analysis (chi-square). **Sample Size Considerations:** As this is a proof-of-concept study, it will likely not be powered to detect belnacasan - placebo differences that are clinically meaningful. For example, the observed difference in endpoint rate ratios would need to be over 60% to achieve 80% power with an alpha error rate of 5% for 20 subjects in each group. This study will provide an estimate of the belnacasan effect size to inform a larger trial where a more clinically meaningful difference can be detected. **Initial Date** November 2021 **Completion Date** April 2022

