
3 OBJECTIVES AND ENDPOINTS

3.1 Primary Objective

To determine the *safety and tolerability* of belnacasan (VX-765/RVT-201/MSR-001) administered orally for 28 days in subjects with mild to moderate COVID-19 as determined by *Adverse Events* and *Serious Adverse Events*.

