3.2 Primary Endpoint

Incidence of Adverse Events and Serious Adverse Events assessed out to day 60.

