7.15 Stopping Rules

Should two or more subjects develop a similar Grade 3 SAE that is at least possibly related to belnacasan or should one or more subjects develop a ≥ Grade 4 SAE that is at least possibly related to belnacasan, the trial will be paused for DSMB safety review.

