8.4 Safety & Tolerability Analyses

All safety & tolerability analyses will be performed on the Safety Population. The safety data will be presented in individual listings and summary tables.

Overall safety will be assessed by the number of belnacasan VX-765/RVT-201/MSR-001 dosed subjects experiencing a grade 4 or 5 SAE during the trial. Of 20 subjects enrolled in the belnacasan group, 3 or more developing a grade 4 or 5 SAE probably related to belnacasan would be

considered unlikely due to chance. Therefore, belnacasan will be determined safe if no more than

2 subjects develop a grade 4 or 5 SAE in the belnacasan group probably related to belnacasan.

In terms of stopping rules, should two or more subjects develop a similar Grade 3 SAE that is at

least possibly related to belnacasan or should one or more subjects develop a \geq Grade 4 SAE that

is at least possibly related to belnacasan, the trial will be paused for DSMB safety review.

Primary Endpoint Analysis

Primary endpoints of adverse and serious adverse events (AE/SAE) will be assessed by Poisson

regression for count data. Events will be counted out to 60 days from randomization to belnacasan

or placebo groups. Because some subjects may be followed for less than 60 days, subject follow-

up time will be included in the Poisson regression as the exposure time variable. If counts are not

Poisson-distributed, either over- or under-dispersed, negative binomial regression will be to

analyze AE/SAE events with appropriate adjustment for over/under dispersion. Comparison of

belnacasan vs. placebo will be expressed as the incidence rate ratio (IRR).

Adverse Events

AEs will be coded according to the latest version of the Medical Dictionary for Regulatory

Activities (MedDRA). The intensity/severity of AEs will be graded according to NCI-CTCAE (see

Section 7.3).

TEAEs, AEs leading to study treatment discontinuation, AEs leading to dose interruption, AEs

related to study medication, SAEs, and AEs leading to death will be summarized by system organ

class, preferred term, and study period. A summary of AEs that are CTCAE Grade 3 or higher, as

well as the most frequent preferred terms, will be provided.

If a subject experiences the same adverse events multiple times within a period, then the event will

be counted only once within the period and by greatest severity.

Descriptive statistics will be used to summarize the safety data.

Clinical Laboratory Values

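### The rule for declaring belnacasan safe reads one count from one arm, so it could return safe while the planned AE/SAE comparison with placebo shows harm

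*Combined protocol and SAP*

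**What the plan says.** **Objective and endpoint.** Section 3.1 sets out to determine the safety and tolerability of belnacasan from AEs and SAEs. Section 3.2 gives the primary endpoint as "Incidence of Adverse Events and Serious Adverse Events assessed out to day 60".

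**Primary analysis.** Section 8.4 states: "Primary endpoints of adverse and serious adverse events (AE/SAE) will be assessed by Poisson" regression, with follow-up time as exposure and negative binomial regression if the counts are not Poisson-distributed. The comparison with placebo is expressed as an IRR. No threshold or conclusion is attached to it.

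**Safety verdict.** The Synopsis (Statistical Considerations) says "Overall safety will be assessed by the number of belnacasan dosed subjects experiencing a grade 4 or 5 SAE during the trial". It then says that, of 20 subjects, "3 or more developing grade 4 or 5 SAE probably related to belnacasan would be considered unlikely due to chance", and that belnacasan will therefore be "determined safe if no more than 2 subjects develop a grade 4 or 5 SAE in the belnacasan group probably related to belnacasan". Section 8.4 repeats this almost word for word.

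**Pause rule.** Under section 7.15, the trial is paused for DSMB review if "two or more subjects develop a similar Grade 3 SAE that is at least possibly related to belnacasan", or if one or more subjects have an at least possibly related SAE of grade 4 or higher.

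**Other safety data.** Section 8.4 plans summaries of AEs leading to discontinuation or dose interruption, AEs related to study medication, SAEs, and AEs of grade 3 or higher. None is connected to the safe verdict.

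**The concern.** The trial randomizes 20 against 20 so that AEs on belnacasan can be set against AEs on placebo in people who are ill with COVID-19. The one sentence that turns data into a safety conclusion makes no use of that comparison. It takes a single count from the belnacasan arm, filtered by grade (4 or 5) and by the investigator's causality rating (probable).

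The plan also pulls in two directions. A second similar grade 3 SAE, or a single grade 4 SAE rated only possible, is serious enough to pause the trial. Yet neither kind of event, however many occur, can change the final verdict.

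At stake is the message carried into the larger trial that section 8.7 says this study will inform. A pre-specified label of safe could stand beside an IRR and tables that point the other way, and the plan does not say how the two would be reconciled.

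**Working it through.** **Step 1. The plan's own cut-off.** The plan calls 3 or more of 20 unlikely due to chance, but gives no reference rate and no error level for that statement. With X ~ Binomial(20, p), where p is the true rate of probably related grade 4/5 SAEs, P(X ≥ 3) = 1 − Σ C(20,x) pˣ (1−p)²⁰⁻ˣ, summed over x = 0 to 2. The values of p below are assumptions.

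| True rate p | P(X ≥ 3) | P(X ≤ 2), verdict safe |
|---|---|---|
| 1% | 0.0010 | 0.9990 |
| 3% | 0.0210 | 0.9790 |
| 5% | 0.0755 | 0.9245 |
| 10% | 0.3231 | 0.6769 |
| 20% | 0.7939 | 0.2061 |

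P(X ≥ 3) is below 5% only if p is at most about 4.2%. The statement cannot be reproduced without a reference rate. The table also shows that the rule does respond to the events it counts.

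**Step 2. What the verdict reads.**

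| Item | Where planned | Input to the verdict? |
|---|---|---|
| Belnacasan subjects with a probably related grade 4/5 SAE | Synopsis, 8.4 | Yes |
| Grade 4/5 SAEs rated possible | 7.8, 7.15 | No |
| Grade 3 SAEs | 7.15, 8.4 summaries | No |
| AE and SAE IRR against placebo | 8.4 | No |
| Any placebo-arm result | 8.4 | No |
| AEs leading to discontinuation or interruption | 8.4 summaries | No |

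No other section adds a condition. Section 4 repeats only the expectation of no more than 2 in 20 and the pause rule.

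**Step 3. Outcomes that would show harm and still be called safe.** The event counts are assumptions, since the documents give no AE rates. Each case supposes that at most 2 belnacasan subjects have a probably related grade 4/5 SAE.

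- *All AEs, 80 against 40, equal follow-up.* IRR = 80/40 = 2.0. SE(log IRR) = √(1/80 + 1/40) = 0.194. 95% CI = exp(0.693 ± 1.96 × 0.194) = 1.37 to 2.92. Exact conditional p = 0.0003.
- *Grade 3 SAEs in 6/20 against 0/20.* Fisher exact two-sided p = 0.020.
- *Grade 4/5 SAEs in 6/20 against 0/20, all rated possible.* The same table, p = 0.020.

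**Step 4. How often the two would disagree.** Assume 2 AEs per placebo subject, a true IRR of 2, and total AE counts independent of the grade 4/5 count. Poisson power = Φ(0.693/0.194 − 1.96) = 0.947. Multiplying by P(X ≤ 2) gives the chance of a significant IRR together with a safe verdict:

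- p = 2%: 0.947 × 0.9929 = 0.94
- p = 5%: 0.947 × 0.9245 = 0.88
- p = 10%: 0.947 × 0.6769 = 0.64

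A simulation using the exact conditional test agreed (0.94, 0.88 and 0.65). If AE counts are overdispersed with negative binomial dispersion 0.5, SE = √[(1/2 + 0.5)/20 + (1/4 + 0.5)/20] = 0.296. Power then falls to 0.649, and the first figure becomes 0.649 × 0.9929 = 0.64.

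**Step 5. Would a significance rule on the IRR do better?** Suppose safe were withheld only when the lower 95% limit of the IRR exceeds 1. With 5 against 0 SAEs and equal exposure, the exact lower limit for the belnacasan share of events is 0.025^(1/5) = 0.478, so the lower IRR limit is 0.478/0.522 = 0.92. Five SAEs against none would not trip that rule. If all five were probably related grade 4/5 events in different subjects, the present rule would already have withheld safe at the third.

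**The case against.** Several points in the plan's favour stand, and they limit how far the criticism goes.

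- A reader might infer that the verdict ignores the primary endpoint altogether. It does not: grade 4/5 SAEs are part of the AE/SAE data. What is missing is any link to the primary analysis, the IRR against placebo.
- A reader might infer that the randomized comparison has no influence on the trial's conclusions. The documents do not say so. The IRR would be reported beside the count, the study is described as hypothesis generating, and no section makes the safe verdict overriding or ties a development decision to it.
- A reader might infer that the verdict is almost settled in advance. That holds only if the true rate is low. The chance of a safe verdict is 0.999 at 1%, but 0.68 at 10% and 0.21 at 20%.
- The rule says safe and never says tolerable. The fair criticism is that no tolerability criterion exists, not that a tolerability verdict disregards the data.
- Runs of grade 3 SAEs would not go unexamined. Section 7.15 pauses the trial, under 7.14 the DSMB reviews all SAEs and decides whether the study can proceed, and 10.13 allows termination for unacceptable risk.

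These safeguards protect subjects during the trial. They do not amend the end-of-trial criterion, which still reads one count.

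**Conclusion.** The concern holds in this form: the safe verdict in the Synopsis and 8.4 depends only on the number of belnacasan subjects with a probably related grade 4/5 SAE. It is unconnected to the planned IRR, to the placebo arm, to grade 3 SAEs and to grade 4/5 SAEs rated possible, and tolerability has no criterion. Following the plan as written could therefore produce a statement of safe alongside randomized evidence of harm.

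That structural finding rests on the text alone. Its size rests on assumed rates. With AEs doubling from 2 to 4 per subject and a 2% rate of qualifying SAEs, the conflict would arise about 94% of the time under Poisson counts and about 64% with dispersion 0.5. It becomes less frequent as the qualifying rate rises. The wording should be corrected, but the data collection and the primary analysis model need no change on this account.

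**What to change.** In the Synopsis and section 8.4:

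1. Delete the sentence that declares belnacasan safe when no more than 2 subjects qualify.
2. State that the safety and tolerability conclusion will be drawn from the AE and SAE IRRs with 95% CIs (exact methods when an arm has zero events), together with by-arm counts and risk differences with CIs for grade 3 or higher SAEs and for study drug discontinuation due to AEs.
3. Keep the related grade 4/5 SAE count, with its exact CI, as a reported item, and keep 3 or more as a flagged safety signal. Say which causality ratings count: section 7.8 lists probable and definite separately, while the rule names only probable.
4. Do not add a significance-based rule for declaring safety. Step 5 shows why, and section 8.7 already says the trial is unlikely to be powered for clinically meaningful differences.

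The DSMB pause rule is left as it is. The cost is a wording amendment and a few extra interval estimates from data already collected. The one loss is the single-line yes/no verdict.

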4 SAFETY AND TOLERABILITY

The drug in an oral form has been used in nearly one hundred patients without a history of major side effects. During the trial, it is therefore anticipated that no more than 2 subjects out of 20 will have an adverse event of grade 4 or 5 that is probably related to belnacasan (VX-765/RVT-201/MSR-001). In terms of stopping rules, should two or more subjects develop a similar Grade 3 SAE that is at least possibly related to belnacasan or should one or more subjects develop a \geq Grade 4 SAE that is at least possibly related to belnacasan, the trial will be paused for DSMB safety review. Safety Monitoring processes are identified in Section 7.14.

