Subjects will be watched carefully for signs of previously documented symptoms in human patients that have received belnacasan (VX-765/RVT-201/MSR-001), as well as symptoms to indicate a drug reaction or new symptoms that could be temporally attributable to the drug. The most frequent adverse effects in humans have been mild and mainly include headache, nausea, lethargy and dizziness. No serious side effects have been described in human and animal studies.

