7.14 Safety Monitoring

A Data Safety and Monitoring Board (DSMB) will be established to monitor the safety of the subjects during the study. The DSMB includes members who are independent of this study and its Sponsor Team, and with relevant clinical expertise, including a good understanding of the safety

of medications for respiratory illnesses. These members may include one or more of the followinga statistician, an infectious disease specialist and/or a pulmonologist. The methodology and the operating procedures for the safety reviews will be developed by the infectious disease specialist and/or pulmonologist in collaboration with the Investigator and will be documented in the DSMB Charter. They will review all SAEs and determine whether the study can proceed or whether protocol modifications are required. The Charter will be submitted to the IND before the trial would commence.

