10.13 Study Termination

This study may be prematurely terminated, if in the opinion of the Investigator or MedStar Health there is sufficient reasonable cause. Circumstances that may warrant termination include, but are not limited to:

- Determination of unexpected, significant, or unacceptable risk to subjects.
- Failure to enroll subjects at an acceptable rate.
- Insufficient adherence to protocol requirements.
- Insufficient complete and/or evaluable data.
- Plans to modify, suspend, or discontinue the development of belnacasan (VX-765/RVT-201/MST-001).

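### Two or fewer probably related grade 4 or 5 SAEs in 20 subjects cannot support the planned verdict that belnacasan is safe: 2 of 20 leaves rates up to about 32% not excluded

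*Combined protocol and SAP*

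**What the plan says.** The primary objective (Section 3.1) is to determine safety and tolerability from AEs and SAEs. The Synopsis (Statistical Considerations, primary safety analysis) turns this into a rule on the belnacasan arm alone. Its premise is that, of 20 subjects, "3 or more developing grade 4 or 5 SAE probably related to belnacasan would be considered unlikely due to chance". Its conclusion is that "belnacasan will be determined safe if no more than 2 subjects develop a grade 4 or 5 SAE in the belnacasan group", again limited to events probably related to the drug. Section 8.4 repeats both sentences and joins them as an inference: "Therefore, belnacasan will be determined safe if no more than" 2 subjects have such an event.

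Four other places bear on the rule:

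- Section 4 gives the background to the cut-off. The oral drug has been "used in nearly one hundred patients without a history of major side effects", and for that reason no more than 2 of 20 subjects are expected to have a probably related grade 4 or 5 event. Section 7.2 adds: "No serious side effects have been described in human and animal studies".
- Section 8.4 also analyses AE and SAE counts by Poisson regression and reports an incidence rate ratio (IRR) against placebo. No threshold is attached to the IRR, and it is not tied to the verdict.
- Sections 4, 7.15 and 8.4 pause the trial for DSMB review after one SAE of grade 4 or higher that is at least possibly related, or two similar grade 3 SAEs. Of the DSMB, Section 7.14 says: "They will review all SAEs and determine whether the study can proceed or whether protocol modifications are required".
- Section 10.13 lets the trial end early for reasons that include "Determination of unexpected, significant, or unacceptable risk to subjects".

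No reference rate, unacceptable rate, alpha or confidence interval is given for the rule. The 5% alpha in Section 8.7 refers to endpoint rate ratios.

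**The concern.** The rule reasons from the absence of a surprising excess to a positive finding of safety. These are different claims. A count of 3 or more may be evidence against a low reference rate, but a count of 2 or fewer is compatible with that low rate and with much higher ones. To conclude safety, the data would have to exclude some rate judged too high, and the plan names none.

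This matters because it is the only text in the plan that converts data into a conclusion on the primary objective. The IRR has no decision attached, and the pause rule governs how the trial is run. A team following the plan to the letter could report that the drug was determined safe with respect to life-threatening and fatal events, on evidence that 20 subjects cannot supply, and carry that statement into the larger trial that this one is meant to inform.

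**Working it through.** **Inputs.** n = 20 in the belnacasan arm; pass if X ≤ 2, where X is the number of subjects with a probably related grade 4 or 5 SAE (Synopsis and Section 8.4). The documents give no true or reference rate, so the rates p below are illustrative. X is taken as binomial(20, p).

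**Step 1: the premise.** The plan attaches no figure to it, so it cannot be reproduced, only evaluated over a range of p:

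P(X ≥ 3) = 1 − [(1−p)^20 + 20p(1−p)^19 + 190p²(1−p)^18]

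| p | P(X ≥ 3) |
|---|---|
| 1% | 0.001 |
| 3% | 0.021 |
| 4% | 0.044 |
| 5% | 0.075 |
| 10% | 0.32 |

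Setting P(X ≥ 3) = 0.05 gives p = 4.2%. At a 5% level, 3 or more events are improbable only if the reference rate is below about 4.2%.

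**Step 2: what a passing result excludes.** The Clopper-Pearson upper limit is the p at which P(X ≤ x) = 0.025 (two-sided 95%) or 0.05 (one-sided 95%). For x = 0 it has a closed form: 1 − 0.025^(1/20) = 16.8% and 1 − 0.05^(1/20) = 13.9%.

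| Events | Two-sided 95% interval | One-sided 95% upper limit |
|---|---|---|
| 0/20 | 0 to 16.8% | 13.9% |
| 1/20 | 0.1% to 24.9% | 21.6% |
| 2/20 | 1.2% to 31.7% | 28.3% |

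The Wilson upper limit for 2/20 is 30.1%, so the choice of interval does not change the picture.

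**Step 3: how often the rule passes, given 20 treated.** At p = 10%: 0.1216 + 0.2702 + 0.2852 = 0.677 (after rounding).

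| True rate | P(X ≤ 2) |
|---|---|
| 5% | 0.92 |
| 10% | 0.68 |
| 15% | 0.40 |
| 20% | 0.21 |

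Passing and failing are equally likely at p = 13.1%.

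**Step 4: if fewer than 20 are treated.** The rule is a count and does not require 20 treated subjects. At p = 20%, P(X ≤ 2) is 0.21 with n = 20, 0.40 with n = 15 and 0.68 with n = 10. If the trial ended early with 2 or fewer events, the wording would still be met, and on weaker evidence.

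**The case against.** The strongest defence has three parts.

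*The trial is proof of concept, and other safeguards exist.* The primary endpoint has its own comparison with placebo, SAE listings and summaries of related and grade 3 or higher events are planned, and any probably related grade 4 or 5 SAE triggers a DSMB pause. This stands to the extent that the defect is confined to one concluding statement and leaves the data, design, subject protection and primary model intact. It does not repair the statement. The DSMB may let the trial proceed after each pause, and the count rule would then still return a verdict of safe. The IRR does not enter that verdict.

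*Prior experience supports a low reference rate.* Section 4 does link the cut-off, qualitatively, to nearly one hundred earlier patients. If one assumes 0 such events in 100 (the documents do not give the count in these terms), the exact upper limit is 1 − 0.05^(1/100) = 3.0% one-sided or 1 − 0.025^(1/100) = 3.6% two-sided. Both are below 4.2%, so the premise can be defended. A reader might infer that the cut-off has no basis at all; Section 4 does not support that. Nor does it support reading the expectation of no more than 2 of 20 as a 10% reference rate, since it caps an anticipated count and states no rate. Accepting the premise still leaves the step from 2 or fewer events to safe unsupported.

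*The rule does exclude something.* Two of 20 excludes rates above about 28% (one-sided) or 32% (two-sided). A reader might infer that the inference fails whatever rate is chosen. That goes too far: it would succeed if the rate to be excluded lay above those limits. The plan does not say that it does.

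**Conclusion.** The plan is wrong as written on this point. The verdict of safe does not follow from 2 or fewer events in 20, because passing results leave true rates of up to 16.8%, 24.9% or 31.7% (0, 1 or 2 events) not excluded, and no rate to be excluded is stated. The premise also lacks a reference rate and alpha, although prior experience may be able to supply the former.

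The interval limits assume 20 treated subjects with independent outcomes. The pass probabilities rest on illustrative true rates and are conditional on 20 treated. A reader might take them as upper bounds, on the view that an early stop means no verdict. The plan does not say so, and Step 4 shows that the pass probability rises when fewer are treated. Nor does the calculation show that belnacasan is unsafe; it shows only that this rule cannot establish the opposite. Which rate would be acceptable is for the sponsor and the DSMB.

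**What to change.** In the Synopsis and Section 8.4, delete the clause that declares the drug safe. In its place, commit to reporting, by arm, the number and percentage of subjects with a grade 4 or 5 SAE, including those probably related to belnacasan, each with a two-sided exact (Clopper-Pearson) 95% interval, alongside the planned IRR. State that with 20 treated subjects, 0, 1 or 2 events do not exclude true rates up to 17%, 25% or 32%.

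If the cut-off of 2 is kept, call it a descriptive flag and not a finding of safety. Give its reference rate with source, its alpha, and its pass probabilities conditional on the number treated.

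Leave the pause rule and the Poisson model as they are. Optional clarifications, not needed to cure the error, are all-cause and at-least-possibly-related tabulations, wording that makes clear that definitely related events also count, and reconciling the term adverse event in Section 4 with SAE in Section 8.4.

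The cost is a few sentences and a few exact intervals, with no new data or subjects. The downside is that the stated safety conclusion becomes less favourable.

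### The safety verdict is a bare count of 2 or fewer, so it still returns 'safe' if a DSMB pause becomes a permanent safety termination after one or two qualifying SAEs, or if so few events come from fewer than 20 dosed subjects

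*Combined protocol and SAP*

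**What the plan says.** **The verdict.** The Synopsis (Primary Safety and Tolerability Analysis) and Section 8.4 give a premise and then a rule. The premise, stated for a belnacasan arm of 20, is that "3 or more developing grade 4 or 5 SAE probably related to belnacasan would be considered unlikely due to chance". The rule follows: "belnacasan will be determined safe if no more than 2 subjects develop a grade 4 or 5 SAE in the belnacasan group probably related", meaning related to the study drug. Section 4 anticipates the same limit, "no more than 2 subjects out of 20 will have an adverse event of grade 4 or 5 that is probably related", but counts adverse events and not SAEs.

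**The pause.** Section 7.15, repeated in the Synopsis and Sections 4 and 8.4, provides that "should one or more subjects develop a ≥ Grade 4 SAE that is at least possibly related to belnacasan, the trial will be paused". The purpose of the pause is a review by the DSMB. Two or more similar grade 3 SAEs, at least possibly related, are a second trigger.

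**After the pause.** Under Section 7.14 the DSMB reviews all SAEs to "determine whether the study can proceed or whether protocol modifications are required". Section 10.13 allows early termination for unacceptable risk, and Section 5.3 allows MedStar Health or a regulator to end the study for safety. None of these sections mentions the safety verdict, and the verdict mentions none of them.

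**Attribution.** Section 7.8 grades causality as not related, remote, possible, probable or definite.

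**The concern.** The verdict depends on a count, and the monitoring process can cut that count short. Every event that moves the count towards 3 also pauses the trial and puts its continuation before the DSMB. If that review ends the trial after one or two events, the count stays at 1 or 2 and the written rule still yields a finding of safety.

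Safety and tolerability is the primary objective, and this is the only pre-specified rule that yields a yes-or-no safety verdict. The plan could therefore attach the label to a drug whose trial had just been terminated for harm. The same gap lets the label rest on far fewer than the 20 subjects from which the cut-off was reasoned.

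**Working it through.** **1. The plan's own figure.** The cut-off of 3 or more of 20 is called unlikely by chance, but no background rate or error level is given, so it can be neither reproduced nor refuted. For X ~ Binomial(20, p), P(X ≥ 3) is 0.001 at p = 1%, 0.007 at 2%, 0.044 at 4%, 0.075 at 5% and 0.323 at 10%. It stays at or below 0.05 only if p is about 4.2% or less.

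**2. Do the two rules count the same events?** On the Section 7.8 scale, probable lies above possible. A probably related grade 4 or 5 SAE therefore always meets the trigger "one or more subjects develop a ≥ Grade 4 SAE that is at least possibly related to belnacasan". The converse fails: an event rated only possible triggers the pause but never counts towards the verdict. Read literally, a definite event is not named in the verdict at all.

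**3. Applying the verdict as written.**
- Pause lifted, all 20 dosed, 1 or 2 events: safe. This is the case the premise describes.
- Trial terminated for safety after 1 or 2 events: still safe.
- Fewer than 20 dosed for another reason, 1 or 2 events: still safe. With fewer than 3 dosed, a count of 3 is impossible.

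**4. What 2 events mean in a smaller group.** The exact (Clopper-Pearson) two-sided 95% upper limit is the 0.975 quantile of Beta(x + 1, n − x), with x = 2.

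| Dosed (n) | Observed rate | Upper limit |
|---|---|---|
| 20 | 10% | 31.7% |
| 15 | 13.3% | 40.5% |
| 10 | 20% | 55.6% |
| 5 | 40% | 85.3% |

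All four pass.

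**5. Illustration of lost discrimination.** Assume independent events, a stop probability s at each pause, a new pause at each qualifying event, and no further events once the trial stops. A third event then requires surviving two pauses:

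P(safe) = 1 − P(X ≥ 3) × (1 − s)².

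For s = 0.5 and p = 10%: 1 − 0.3231 × 0.25 = 0.919.

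| True rate | P(X ≥ 3) | No stopping, 20 dosed | s = 0.5 | s = 0.8 |
|---|---|---|---|---|
| 10% | 0.323 | 68% | 92% | 98.7% |
| 20% | 0.794 | 21% | 80% | 96.8% |
| 30% | 0.965 | 4% | 76% | 96.1% |

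As p approaches 100%, P(safe) falls no lower than 1 − (1 − s)², which is 75% at s = 0.5 and 96% at s = 0.8. If the DSMB always stops at the first or second event, P(safe) is 100% at every rate.

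**6. Allowing for subjects already dosed.** Section 9 expects enrollment over 3 to 6 months. Taking these as about 91 and 182 days, with even accrual of 20 belnacasan subjects and 28 days of dosing, the number on drug at any time is about 20 × 28/91 = 6.2 or 20 × 28/182 = 3.1. Suppose the first event stops the trial with six others on drug, each with residual risk q. The verdict is safe if at most one more has an event:

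(1 − q)⁶ + 6q(1 − q)⁵.

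- With q = p/2: 97%, 89% and 78% at p = 10%, 20% and 30%.
- With q = p: 89%, 66% and 42%.

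The matching figures with no stopping, given at least one event among 20, are 63%, 20% and 3%. The loss of discrimination is smaller than in step 5 but remains.

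**The case against.** - **The trigger is a pause, not a halt.** The text says "the trial will be paused for DSMB safety review". A trial may pause, resume, dose all 20 and end with one or two events. A reader might infer that the two thresholds contradict each other. They do not: a sensitive interim trigger can sit beside a looser final criterion. This stands, and it narrows the point to a pause that becomes permanent.
- **The rule is reasoned from 20 subjects.** On this view, early termination is simply not addressed. That stands only in part. The 20 motivates the cut-off, but the sentence that delivers the verdict has no denominator and no exception, so a literal reading gives a definite and wrong answer.
- **The stop probabilities are invented.** They are. The documents give none, and the DSMB Charter that will hold the operating procedures is not part of them. Section 7.15 also does not say whether a pause stops enrollment, dosing or both, or whether each later event causes a new pause. The percentages are illustrations only.
- **A reader might infer that the rule runs backwards,** with a more toxic drug more surely called safe. The figures do not support this: at a fixed stop probability below 1, P(safe) falls as the true rate rises, though only to a high floor.
- **A reader might infer that the whole primary analysis fails.** It does not. The primary endpoint analysis in Section 8.4 is a Poisson regression against placebo with follow-up time as exposure, reported as an incidence rate ratio. It does not use the count rule and accommodates shortened follow-up.

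**Conclusion.** The point holds in limited form. Taken literally, the verdict ignores both a safety termination and a reduced group, and would return safe after one or two probably related grade 4 or 5 SAEs in either case. That follows from the text alone and needs no assumption about rates.

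Its size depends on how often a pause becomes permanent, which the documents do not say. If stopping is even moderately likely, the criterion discriminates poorly: roughly 92%, 80% and 76% against 68%, 21% and 4% under the step 5 assumptions, with a smaller gap once later events in dosed subjects are allowed for. Nothing here faults the pause rule, and the incidence rate ratio analysis is unaffected.

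**What to change.** Add to Section 8.4 and the Synopsis:

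> If the trial is terminated, or a safety pause is not lifted, because of belnacasan-related SAEs, the safety criterion is not met regardless of the count. If fewer than 20 belnacasan subjects are dosed for any other reason, 3 or more qualifying events still means the criterion is not met; with 2 or fewer, no determination of safety is made, and events over number dosed are reported with an exact confidence interval.

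Dosed should mean at least one dose received, as in the Section 8.1 safety population, so that ordinary early discontinuation of study drug does not disable the rule. A trial closed for slow enrollment with 3 qualifying events would still receive its adverse verdict.

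Reconcile the attribution wording of the two rules (at least possibly against probably, with definite not named), and the adverse event in Section 4 with the SAE in Section 8.4. Which level applies is for the sponsor to decide.

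The pause rule, the clinical thresholds and trial conduct are unchanged. The cost is a short text amendment, and the safe label becomes unavailable after a safety termination or with a reduced group.
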